3. STUDY DESIGN

To address the primary and secondary hypotheses, this research study was designed as a randomized clinical trial comparing the manualized FORT-A treatment to treatment as usual for polytraumatic chronic musculoskeletal pain in the STVHCS Polytrauma Rehabilitation Center. Eligible OEF/OIF/OND Veterans will be randomized to either arm in 1:1 random permuted block randomization with no stratification. Because the FORT-A is a group intervention, it is vital that we randomize into meaningful blocks of at least three Veterans and no more than seven. Three is chosen as the lower block boundary because the PI had success in the original FORT trial with FORT groups of three active duty service members. Seven Veterans will be the upper boundary because FORT groups of more than seven military members were difficult to manage. In block randomization with static boundaries, study staff overseeing randomization will lose blinding if they are aware of how many participants have already been randomized into each block. For example, if block boundaries are always 5 participants and the treatment as usual condition has 5 participants while the active treatment has 4, then the staff randomizing the 10th participant will know with certainty that this participant will be in the active treatment group. To protect blinding, we have chosen to implement a variable boundary randomization for which the study staff randomizing patients will be blind to the boundaries and the resulting condition of the participant (see Sanghaei, 2011). The PI, Independent Evaluators, and Biostatistician will be blind to the condition of all participants until data lock. A research assistant overseeing randomization will also be blinded by randomizing unique patient identifiers into variable permuted blocks (through the STRONG STAR Data Core) by unique study identifier (e.g., first participant identified as #0001). All assessments given by Independent Evaluators will be labeled with just the unique identifier. Only the study coordinator (and co-coordinator) will be able to link unique identifiers to individual participants.

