Pain Intensity	Numeric Rating Scale (NRS)	Assessed at every assessment interval and at every physical therapy appointment for FORT-A participants Opinions vary on a clinically meaningful change in pain numeric rating, but many agree that an increase in pain rating > 2 points is clinically significant (see [name] et al., 2006)
Emotional Distress	PHQ-9	Given at every assessment interval and once a week during group treatment

		
sessions for FORT-A participants
 
Change in PHQ-9 scores is clinically significant if the total score rises above 15 (as defined in Kroenke & Spitzer, 2002). Those who begin the study with a score above 15 show significant change (requiring AE report) if the score rises 5 points or more. If item #9 increases at all, this will be reported an AE. An increase of Item #9 by 2 points or more will be considered a SAE.

Opiate Withdrawal	SOWS	
The Subjective Opiate Withdrawal Scale will be given to all FORT-A participants once a week during treatment and at all assessment intervals for all follow-up intervals. A SOWS score of 11 or more will indicate an AE requiring follow-up (based on established cut-off scores).

This study maintains a weekly research meeting (starting September 2015; currently set for Thursday morning from 1030-1100 at the STRONG STAR Conference Room with an open phone line for those who need to call into the meeting) to discuss research progress and to discuss participant status and flow throughout the research process. All Adverse Events (AEs) and Serious Adverse (SAEs) will be discussed at these meetings (attended by all study staff). To protect blinding, participants will be discussed by unique identifier only.

AE reporting procedures (as described in the attached SOP) will begin immediately after an AE is noticed and will be reported to the IRB after discussion at the weekly research meeting. SAEs must be reported to the IRB within 24-48 hours. If a protocol deviation, SAE or UPIRSO is not reported within 48 hours, a reason will need to be documented on the P50 form.

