We will enroll $n = 65$ ($N = 130$) and anticipate $\leq 30\%$ all-source attrition rate as in our previous study. Assuming that at the 12-month follow-up the standard care treatment arm will report mean (SD) ODI scores of 19.5 (6.6), using a two-tailed $\alpha = 0.05$, we will have power = 0.80 to detect effect sizes as small as $d = 0.50$. For the ODI, this is equivalent to a clinically meaningful 3.3 point difference between groups. In our original FORT trial, we observed a 9.2 point difference between individuals who were not lost to follow-up at 12-months. Thus, for the intention-to-treat analyses, where we expect that up to 30% of individuals will require imputation of some kind, our expected effect sizes can be attenuated by $\sim 60\%$ with sufficient power to detect a clinically meaningful difference. Differences smaller than 3.3 points on the ODI are unlikely to be clinically meaningful.

Treatment Assignment Procedures

Participants will be randomly assigned to each of the study arms based on the rationale and procedures outlined in sections 6.2.2 and 6.2.3 of this protocol. Masking will be managed using the diagram shown in Figure 2. Pursuant to this diagram, masking will be overseen and maintained through a collaboration between the study coordinator (who will not be blind to any part of this study to all for better tracking of participant flow and AEs; though the Coordinator will not take part in any evaluations and is forbidden to discuss blinded information with any study team member without first discussing it with the PI and the STRONG STAR Administrative Core) and the STRONG STAR Data Core (which maintains the link between identity and participant number). Masking of treatment arm to the participant or provider is absolutely impossible in a behavioral trial. Plans for

retention of the blind are described in sections 5.2, 5.4, and 6.2.3.1 of this protocol. If a blind must be broken (e.g, to protect the safety of a participant), then the blind can only be broken by the study Coordinator and/or Co-Coordinator after consultation and permission from the PI and the STRONG STAR Admin Core. To break the blind, the Coordinator will contact the STRONG STAR Data Core and request revelation of the participant identity and linked unique identifier.

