9.4 Interim Analyses and Stopping Rules

Interim analyses will not be completed as part of this research. We were fortunate to have solid data from the original FORT trial to help estimate power for the proposed research, and the resulting power analyses are solid. Thus, we do not anticipate uncovering changes in the primary outcome that would necessitate a need for early stoppage or futility of the proposed research and do not feel that we have any preliminary impetus for spending alpha in pursuit of these interim analyses. In conclusion, we do not anticipate observing evidence for early futility or superiority in this trial until all data are gathered in accordance with our in-place power analysis.

The interventions used in this study have been thoroughly studied in other research and it is predicted that the need for a safety review will be low. However, there are some circumstances that would require suspension of study activity and review of safety by an ad hoc safety review committee as follows:

- This is one of the first studies of an interdisciplinary pain program for chronic pain and trauma polymorbidity. The PIs STRONG STAR Pain and PTSD Study revealed no significant exacerbation of PTSD symptoms in a combined pain and PTSD protocol, but PT was not involved in that protocol. There is no reason right now to believe that Physical Therapy will exacerbate PTSD symptoms, but if this were to occur (based on a 20 point increase on the PCL-5) then a safety review would be needed to determine if the study must stop. This finding would also need to be adjudicated through the AE process.
- As noted above, opioid withdrawal effects will be monitored, and a score above 11 on the SOWS will require safety review.
- If physical injury or emotional disruption AEs accumulate (more than 4 minor; easily recovered within one day – or 2 major; requiring more than ASAP intervention to stabilize) then a safety review will be in order.

Such findings are presented to the study statistician or to the Independent Monitoring Committee (IMC) statistician to review the events by group to determine whether there are statistical as well as clinical concerns. The statistician reports his findings to a closed session of the IMC or to the Safety Officer and/or NCCIH. The findings are used to determine what steps will be taken.

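### Section 9.4 allows the study statistician to review safety events by group, although Section 3 keeps the Biostatistician blind until data lock

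*Combined protocol and SAP*

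**What the plan says.** Section 3 (Study Design) sets the blind: "The PI, Independent Evaluators, and Biostatistician will be blind to the condition of all participants until data lock". It makes no exception for safety review.

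Section 9.4 rules out interim analyses ("Interim analyses will not be completed as part of this research") but lists circumstances that call for a safety review. They include a 20-point rise on the PCL-5, an opioid-withdrawal trigger ("a score above 11 on the SOWS will require safety review") and an event count ("If physical injury or emotional disruption AEs accumulate (more than 4 minor; easily recovered within one day", or 2 major events). It then says: "Such findings are presented to the study statistician or to the Independent Monitoring Committee (IMC) statistician to review the events by group". The result goes upward: "The statistician reports his findings to a closed session of the IMC or to the Safety Officer and/or NCCIH".

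Section 9.2 has a general rule for breaking a blind, for example to protect a participant: "the blind can only be broken by the study Coordinator and/or Co-Coordinator after consultation and permission from the PI", together with the consortium's Administrative Core. It does not mention a statistician's review by group.

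**The concern.** Section 9.4 offers the study statistician and the IMC statistician as equal alternatives. The IMC route fits Section 3. The other route gives the person who is meant to stay blind a comparison of events between groups before data lock. Whether the blind holds then depends on which statistician happens to be asked.

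The analyst's blind carries some weight in this trial. Section 9.2 accepts that neither participants nor providers can be masked, and the primary outcome is self-reported. Several choices that affect the results are also still open:

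- Section 9.6 names missing-data sensitivity methods only as examples, to be informed by the patterns of missingness. Section 9.2 expects up to 30% of participants to need some form of imputation, which is 0.30 × 130 = 39 people.
- Section 9.6 says PTSD and depression will be accounted for, but not how.
- Section 5.3.3 says that participants who receive certain outside programmes may have to leave the per-protocol set.

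An analyst who has seen events by arm would make these choices with knowledge that Section 3 intends to withhold.

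**Working it through.** The main check is a comparison of texts. The plan gives no figure to reproduce.

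**1. Same role?** Section 3 says Biostatistician; Section 9.4 says study statistician. No available text treats them as two people, and Section 9.4 contrasts the study statistician only with the IMC's. One role is the natural reading, though it is an inference.

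**2. Is there an exception elsewhere?** Section 9.2 covers disclosure of an individual's identity and assignment by the Coordinator, with permission. It does not cover a table by group. No available text names a separate unblinded statistician or limits the review to coded arms.

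**3. Would coded arms be enough?** Not reliably. Section 7.3 monitors FORT-A participants more closely during treatment: PCL-5 at each individual PTSD session, pain rating at each physical therapy appointment, and PHQ-9 and SOWS weekly. A table labelled A and B could reveal the FORT-A arm through the number and type of its records. Section 7.3 also has adverse events discussed at a weekly meeting of all study staff: "To protect blinding, participants will be discussed by unique identifier only". If the statistician attends, a table by group could be matched to individual identifiers.

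**4. How likely is a triggered review?** The plan gives no event rates, so only ranges can be shown.

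*Minor events.* Inputs: 65 FORT-A participants (Section 9.2) and 12 physical therapy sessions each (Section 5.1). Assumptions: full attendance, independent events, a count taken over the whole trial, and no other source of events.

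- Sessions: 65 × 12 = 780.
- With rate p per session, the mean is m = 780p, and P(more than 4) = 1 − Σ (k = 0 to 4) e^(−m) m^k / k! (Poisson).

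| Assumed rate per session | m | P(more than 4 events) |
|---|---|---|
| 0.1% | 0.78 | 0.1% |
| 0.25% | 1.95 | 5% |
| 0.5% | 3.9 | 35% |
| 1% | 7.8 | 89% |

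*SOWS.* Inputs: four scheduled visits for all 130 participants (Section 6.1), plus weekly use over three treatment weeks for 65 FORT-A participants (Section 7.3). Full retention and independent scores are assumed.

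- Administrations: 130 × 4 + 65 × 3 = 520 + 195 = 715.
- With a proportion q of scores above 11, P(at least one) = 1 − (1 − q)^715.
- q = 0.1% gives 51%; q = 0.5% gives 97%.

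The event-count trigger therefore depends almost entirely on the assumed rate. The SOWS trigger is sensitive even at low rates, and Section 4.1 admits people who have been off opioids for as little as one week. These are chances of a review, not of a breach, because the IMC route may be taken each time.

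**The case against.** The strongest reply is that Section 9.4 asks only for review by group. It does not say that the arms are named or that anyone's assignment is disclosed, and review under codes A and B could satisfy both sections. That reading is open. It is not written down, however, and the uneven monitoring in Section 7.3 makes the code weak protection.

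A second reply is that the deciding documents may lie elsewhere. Sections 6.2.3 and 9.2 refer to Figure 2 for who is blinded to what, and Section 7.6 places safety monitoring under the consortium's monitoring plan and Appendix Q. None of these was available. They may resolve the matter, so they should be checked before anything is changed.

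A reader might also draw three stronger conclusions that the documents do not support:

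- *That the plan requires the analyst to be unblinded.* It does not; the IMC statistician is an equal option.
- *That a by-group review is near certain because the thresholds are low.* Section 9.4 itself predicts little need for safety review. Section 7.2 cites a review of 472,013 military physical therapy visits with no significant adverse effects, while noting that poor surveillance may explain this. At low event rates the count trigger would seldom be met.
- *That the primary result is compromised.* Section 9.6 states the primary comparison in advance as 12-month disability adjusted for baseline, and Section 9.3 states the intent-to-treat population. Tables of injuries, distress or withdrawal scores do not show ODI by arm. PCL-5 triggers bear on a secondary outcome, and then only for the cases reviewed.

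**Conclusion.** The point holds as a conflict between two sections on one permitted route. It rests on two assumptions: that Biostatistician and study statistician are the same role, and that neither Figure 2 nor the monitoring plan restricts what that person sees. If the arms were effectively masked, the conflict would fall away, but the plan does not say that they are.

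The consequence is moderate. It falls on the missing-data sensitivity analyses, covariate handling and per-protocol exclusions, not on the stated primary ANCOVA, and sample size and power are unaffected. No single probability of a review can be defended from the documents. Because the text permits a breach of a stated blind and the repair is cheap, it should be corrected rather than left to practice.

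**What to change.** In Section 9.4, send review of events by group only to the IMC statistician. First confirm that an IMC exists: it is named in Section 9.4 but is missing from the committee list in Section 12, and Section 9.4 also speaks of an ad hoc safety committee. If none is constituted, simply deleting the study statistician would leave nobody identified for the task. In that case name a statistician who takes no part in the final analysis, such as one in the STRONG STAR Biostatistics and Data Core, which already holds the assignments (Section 4.3). The plan does not say whether the trial's Biostatistician belongs to that Core, so the named person must be different.

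State that the study statistician sees pooled safety data only until data lock, and say who supplies the arm labels to the reviewer. Then bring Section 3, the unblinding rule in Section 9.2 and Section 9.4 into agreement, and check them against Figure 2 and the data safety monitoring plan.

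The cost is a few sentences in an amendment and, if there is no IMC, a small amount of an independent statistician's time. The safety triggers need not change.

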9.5 Outcomes

9.5.1 Primary Outcome

The primary outcome for this research is self-reported disability based on the Oswestry Disability Index (ODI). The ODI is a ten-item self-report disability measure assessing an individual's perception of limitation in a number of different life domains due to pain. Each of the ten items asks the participant to use a 0 to 5 numeric rating scale (each with a specific anchor) to rate the extent to which they feel that their functioning is restricted because of their pain. To score the measure, the individual score for each item is summed into a total score and the total score is then divided by 50 and multiplied by 100 to generate a total score ranging from 0 to 100. This total score represents a % disability score which can be categorized as Minimal (0-20%), Moderate (21-40%), Severe (41-60%), Crippled (61-80%), or Bed Bound/Exaggerating (81-100%). The ODI has been cited over 200 times in the scientific research literature with firmly established validity for self-report disability due to chronic pain (Fairbank & Pynsent, 2000). The original ODI (a measure specific to spinal pain) has been updated in Version 2.0 to include extremities in the instructions allowing the measure to validly assess spinal and extremity pain-related disability (Roland & Fairbank, 2000). When compared against the Roland-Morris Disability Questionnaire (another gold-standard spinal disability measure that has been successfully adapted to include extremity pain), the ODI has shown better sensitivity to change at higher levels of disability and is the better measure for this research (Roland & Fairbank, 2000). The ODI can be completed in 5 minutes and scored in one minute.

The ODI will be given at every assessment encounter including screening and will be administered by an IE who is blinded to the randomized condition of the participant. Because this measure is a straightforward, self-report assessment, there is hardly ever a need to adjudicate responses and scoring. However, in some circumstances (e.g., an item is left blank, selection of a response is not clearly marked or covers more than one response) a response will need to be adjudicated between the IE, the Coordinator, and the PI. Meetings for adjudication will occur on an as-needed basis and the Coordinator will ensure that testing materials are not identifiable before discussion with the PI (all assessments will be recorded using only the participant's unique identifier). Adjudication will need to occur within 2 business days from the time that an aberrant or unclear response is noted.

Among the numerous options for pain-related disability assessment, the Oswestry was chosen because of its strength as a predictor of long-term outcome in the original FORT trial and the attention this measure has received in back pain research. The original FORT trial included many outcome measures. Measures of functional capacity were

most responsive to changes (which makes sense based on FORT’s emphasis of function over palliative pain control). We compared 4 functional measures (Floor-to-waist lift [FTW], waist-to-eye level lift [WTE], Oswestry Disability Index [ODI], Million Visual Analog Scale [MVAS]). Of the 4 measures, the ODI produced the strongest correlation to other measures of pain management and adjustment.

Pearson correlation between 4 disability measures and other notable FORT outcomes				
r-value	Floor-to-Waist Lift	Waist-to-Eye Lift	Oswestry Disability Index	Million Visual Analog Scale
Depression	-.174	-.278	.690	.424
Fear Avoidance	-.106	-.184	.622	.530
Pain Rating	-.099	-.219	.856	.816

9.5.2 Secondary Outcomes

There are numerous secondary outcomes for this study that can be meaningfully categorized as physical measures (functional capacity evaluation, Actiwatch), medication (MEMS, timeline followback interview, MQS), psychosocial pain (Pain Catastrophizing Scale) and psychosocial trauma and emotional distress (measures of PTSD, depression, suicide risk, etc.). Because these measurement categories all require separate skillsets for interpretation of problematic or ambiguous results, they must all be adjudicated through separate subcommittees within the study team and the STRONG STAR Consortium as follows:

Physical Measures will be adjudicated by the PI, the Research Coordinator, and [name] (an internationally-recognized expert in Physical Therapy assessment for chronic pain) or a PRC PT/OT. Functional Capacity Evaluation (FCE) data will be recorded by UTHSCSA PT students and/or PRC PT/OT providers and will be discussed with [name] or a PRC PT/OT within two business days after each assessment. Data will be scrutinized by [name] or a PRC PT/OT in raw format and interpretations will be recorded. Any ambiguity in the data will be adjudicated by an assessment sub-committee including the PI, the PT Interventionist(s), and [name] OR a PRC PT/OT. Data will be examined and discussed using unique identifiers only. Actiwatch data will be uploaded by a STRONG STAR IE at pre-treatment and all follow-up assessments and uploaded data will be scrutinized by the IE (who will be trained in the use of the Actiwatch system by the PI – with consultation from the manufacturer if needed) who will identify any aberrations in data that may require adjudication. Actiwatch data will be adjudicated using the same timeframe, methods, and subcommittee as the PT data.

NOTE: Actiwatch was chosen over Actical for this research based on data suggesting that actigraphy offers usable data after 10 days of wear time (Freedson, 2014; Mailey et al., 2014) and that wrist-worn actigraph is more sensitive to intensity of movement

than hip-worn actigraph (Mendoza et al., 2014). Thus, we will use the Actiwatch in 10-day epochs (participants will be asked to wear them for 12 or more hours per day; per Hermann et al., 2012) at every assessment period (instead of continuous wear for 6-months at a time). Previous studies have shown higher rates of adherence using 10-day epochs.

Medication Data will be adjudicated by the PI, the Research Coordinator, and [name] (an expert in trauma and addiction comorbidity). Timeline followback interview and MQS-III data will be discussed for each participant by the IE and the Coordinator within two business days of each assessment. If there are any noted problems with the TLFB data, then the assessment will be adjudicated by the above sub-committee within 2 days of review. MEMS cap data will be gathered for each participant's reported "most helpful" pain medication and any opioid medications they are prescribed by VA or other providers outside the VA system during the course of the study. MEMS data will be downloaded for each participant at each assessment follow-up visit. Upon download, the IE will scrutinize downloaded data to ensure that it falls within an expected range. If aberrant or missing data are noted, these will be adjudicated with the above sub-committee (and potentially discussed with the manufacturer if hardware or software problems are suspected) in a deidentified format.

The primary opioid endpoint will be the timeline followback (TLFB) interview. The TLFB represents the primary measure of opioid use because of its reliability and sensitivity as a daily measure of opioid use and its lack of perceived stigma compared to regular urine tox screen. A trained and masked IE will administer TLFB asking participants about any opioid medication use and use of other medications for pain. The TLFB Interview for this study was adapted from Sobell and Sobell (1992) as a semi-structured clinical interview asking the participant to use a blank calendar to describe the number of pain pills taken each day for 30 days. Instructions are provided to help the interviewer guide the participant in completing the recall as accurately as possible. This method has been reliably used in other trials of medication/opioid use and abuse (Kunoe et al., 2009).

Study personnel blind to participant randomization can use the VA electronic health record (CPRS) to identify active and new opioid medication prescriptions from providers working in the VA system. Study physicians ([name] and [name]) get free access to the Prescription Access in Texas (PAT) prescription monitoring program to examine any and all Schedule II through V medications given by any provider in the State of Texas. Both CPRS and PAT (which maintains records of medications dispensed to a patient for 365 days) will be accessed at each Veteran's one-year follow-up visit to identify medications prescribed over the one-year study participation period.

Psychosocial Trauma and Emotional Measures will be adjudicated through the STRONG STAR Assessment Core using existing SOP for surveillance and adjudication of these measure. STRONG STAR has implemented this process for military and VA studies serving thousands of study participants across dozens of

studies (see Appendix J).

